Investigator being the sole Sponsor has to comply with all regulatory and legal requirements as far as monitoring and data collection is concerned by following the latest Executive Order on Good Clinical Practice for Clinical Trials Involving Human Medicine (In Danish: "Bekendtgørelse om god klinisk praksis i forbindelse med kliniske forsøg med lægemidler på mennesker").

Reporting Procedures for Exchange of Adverse Event Information.

(i) For purposes of this Protocol and Agreement the below terms shall be defined as follows:

"Adverse Event" or "AE" shall mean any untoward medical occurrence in a Study subject who is administered the Study Drug regardless of whether or not a causal relationship with the Study Drug exists. By way of example and without limitation, an AE can be any unfavorable and unintended sign (for example, an abnormal laboratory finding), symptom, or disease temporally associated with the use of the Study Drug.

"Device Deficiency" shall mean inadequacy of a Study Drug device related to its identity, quality, durability, reliability, safety or performance, such as malfunction, misuse or use error and inadequate labeling.

Protocol
The hernia study
September 16. 2016

"Incident" shall mean any malfunction or deterioration in the characteristics and/or performance of a Study Drug device, as well as any inadequacy in the labeling or the instructions for use which, directly or indirectly, might lead to or might have led to the death of a patient, or user, or of other persons or to a serious deterioration in the state of health.

"Medical Device Event" shall mean any malfunction or deterioration in the characteristics and/or the performance of a Study Drug device, as well as any inadequacy in the labeling or the instructions for use which led to or could have led to an untoward event for the user or any other person.

"Serious Adverse Event" or "SAE" shall mean any untoward medical occurrence in a Study subject who is administered the Study Drug that results in death, a life-threatening drug experience, requires inpatient hospitalization or prolongation of existing hospitalization, results in persistent or significant disability/incapacity, or is a congenital anomaly/birth defect, cancer, or is a new cancer if the cancer is the condition of the study, or overdose. Other important medical events that may jeopardize the patient or may require intervention to prevent one of the outcomes listed previously should also be considered "serious".

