"Suspected Unexpected Serious Adverse Reaction" or "SUSAR" shall mean any Serious Adverse Event, the nature, severity or frequency of which is not consistent with information in the most current investigator's brochure, or with respect to a marketed product the most current Summary of Product Characteristics (SPC) or Package Insert.

(ii) Serious Adverse Event and Suspected Unexpected Serious Adverse Reaction, Medical Device Event, Potential Incident, Device Deficiency or Incident Reporting: Principal Investigator shall forward to MSD's Global Safety ("MSD GS") group, any SAE and SUSAR, Medical Device Event, Device Deficiency or Incident information, including, but not limited to, all initial and follow-up information involving any Study subject in the Study. Notification shall be in the form of a completed CIOMS I/MedWatch (or other mutually agreed upon format) within two (2) business days of learning of the information. This information shall be transmitted to MSD GS using the contact information provided below or such other modified contact information as provided by MSD in writing. All information shall be transmitted in the English language and contain the reporter's name and the Study subject identifier code. SUSAR information will be reported unblinded if the Study Drug has been blinded in the Study. Randomization codes for all other SAEs will be provided to MSD GS at end of Study if the Study Drug has been blinded in the Study.

(iii) MSD may define certain Non-Serious Events of Interest. If any Non-Serious Events of Interest are defined, Merck will provide such information in writing to Principal Investigator at the time of Protocol approval, execution of this Agreement or anytime

Protocol
The hernia study
September 16. 2016

thereafter. Reporting of any defined Non-Serious Events of Interest will be handled in the same manner as SAEs unless mutually agreed otherwise in writing by the parties.

- (iv) All reports of Study Drug exposure during pregnancy or lactation (including a female partner of a male Study subject using the Study Drug), whether associated with an AE or not, must be reported to MSD GS in accordance with the timelines and contact information for an SAE. Principal Investigator shall follow pregnancies to term to obtain the outcome of the pregnancy. The outcome of the pregnancy shall be forwarded to MSD GS.

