provided to any inspector. In the event the regulatory authority requests or requires any action to be taken to address any citations, Principal Investigator and Institution agree, after consultation with MSD, to take such action as necessary to address such citations.

F. A copy of all 15 Day Reports and Annual Progress Reports / Development Safety Update Report (DSUR) are to be submitted as required by the applicable regulatory authority by the Principal Investigator. Principal Investigator agrees to cross reference this submission according to local regulations, to the Study Drug number (IND, Clinical Study Authorization (CSA)/EudraCT approval number, etc) at the time of submission. Additionally Principal Investigator agrees to submit a copy of these reports to MSD (Attn: Global Safety; [contact]) at the time of submission to the appropriate regulatory agency.

G. MSD may provide the Principal Investigator and Institution, at Study initiation and on an ongoing basis, with information regarding the Study Drug, including but not limited to safety information. The Principal Investigator and Institution agree to hold this information in confidence.

H. Principal Investigator & Institution accept to follow the latest Executive Order on Good Clinical Practice for Clinical Trials involving Human Medicine (In Danish: Bekendtgørelse om god klinisk praksis i forbindelse med kliniske forsøg med lægemidler på mennesker").

Principal Investigator and Institution accept also to report the serious adverse reactions and unexpected non-serious adverse reactions discovered within 2 working days to MSD att: Pharmacovigilance by [contact].

Side effects/events that will *not* be registered:

In general, side effects and events that are typically seen in connection with the normal course of anesthesia and operation will not be registered and reported to the Danish Medicines Agency. In this protocol side effects/events (AE) will be defined in the form of expected changes in pulse and blood pressure as a result of the anesthesia. Pulse and blood pressure values (measured 3 repeated times within a 10-minute period) that deviate less than +/- 30% of the starting level will thus be accepted and not registered. Side effects/events that may be ascribed to the operation with certainty, for example, pain in the surgical wound or wound infection will not be registered. Side effects/events that with certainty have arisen as a result of the patient's postoperative treatment will

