not be registered.

As reference documents for assessment of whether an SAR is a "suspected unexpected serious adverse reaction" (SUSAR), the Danish Medicines Agency and EMEA's product summary will be used for Sugammadex.

The local investigator reports AR, AE, SAR, SAE and SUSAR to sponsor/ investigator. In the event of SAR/ SAE this happens at once. In the event of SUSAR the coordinating investigator will likewise report at once to sponsor/investigator. Sponsor/investigator will immediately report SUSAR to the Danish Medicines Agency. Within 7 days sponsor/investigator will ensure that all information is registered and reported to the Danish Medicines Agency, as well as what consequences they have for the trial. Eight days after reporting sponsor/investigator will report to the Danish Medicines Agency all relevant information about sponsor/investigator's follow-up to the report. The case file of each individual trial subject will postoperatively be reviewed by the coordinating investigator for the purpose of tracking side effects. All AR, AE, SAR, SAE and SUSAR will be gathered on one list, which sponsor/investigator reports to the Scientific Ethics Committee and the Danish Medicines Agency at the conclusion of the trial. The list will contain all registered side effects/events.

Quality control and quality assurance:

General procedures for quality control and quality assurance will be followed, cf. ICH GCP guidelines. Data will be monitored by the GCP unit. Upon granting of informed consent, authorization will be obtained from the trial subjects for third parties to be able to have access to information on the person in question's health condition. Investigator will thus allow the GCP unit or the Danish Medicines Agency direct access to source data/documents with monitoring, auditing and/or inspection. Concomitant medication and treatment before and during the trial is allowed, if it is not described under the exclusion criteria. A decision on which regular medicine the patient shall continue with before, during and after the operation will be made by the doctors in the department in which the patient is admitted in normal collaboration with doctors from Gentofte

Hospital.

Schedule:

Anticipated start (inclusion of first patient) February 2015. Long term follow-up data (recurrences) will be published separately when data are ready.

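### Events ascribed with certainty to the operation or to postoperative treatment go unregistered, with no exception for serious ones, which conflicts with the plan's own SAE rules

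*Combined protocol and SAP*

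**What the plan says.** The exclusion stands in the combined protocol and SAP under *Side effects/events that will not be registered*. It opens with events typical of a normal anaesthetic and operation, which "will not be registered and reported to the Danish Medicines Agency". A separate sentence then covers "Side effects/events that may be ascribed to the operation with certainty" and continues: "for example, pain in the surgical wound or wound infection will not be registered". The next sentence does the same for events that certainly come from postoperative treatment. Seriousness is not mentioned in any of these sentences.

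Four other sets of rules apply to the same events:

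- *Reporting Procedures for Exchange of Adverse Event Information*, item (i), defines an adverse event "regardless of whether or not a causal relationship with the Study Drug exists". It defines an SAE by outcome; one criterion is that the event "requires inpatient hospitalization or prolongation of existing hospitalization".
- Item (ii) of the same section requires the investigator to forward "any SAE and SUSAR, Medical Device Event, Device Deficiency or Incident information" to the company's safety group within two business days.
- *Registration of adverse events* has all events followed to a final diagnosis or cause, with the result entered on the CRF.
- The last paragraph before *Quality control and quality assurance* covers the local investigator's reports to the sponsor: "In the event of SAR/ SAE this happens at once". It then says that all classes of event, SAEs among them, go on a single list to the ethics committee and the Danish Medicines Agency at the end of the trial. It closes: "The list will contain all registered side effects/events".

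**The concern.** The exclusion works by cause. The SAE rules work by outcome and set cause aside. The two collide for any event that is both serious and clearly surgical, and wound infection is the protocol's own example of a clearly surgical event. Site staff would then hold two opposite instructions for the same case.

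What is at stake is the completeness of the end-of-trial safety list. If that list is compiled from registered events, a serious event left unregistered under the exclusion could be absent from it, even if the same event had been forwarded to the company.

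**Working it through.** The question is one of text, and no figure in the plan bears on it. The check follows one hypothetical case through each rule: a treated patient who is admitted after discharge with a wound infection that is judged certainly due to the operation.

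**Does the case fall under the SAE rules?** Yes. *Surgical method* says the operations are outpatient procedures, so a later inpatient stay for infection meets the hospitalisation criterion. The definitions apply to subjects given the study drug, and both groups are due to receive rocuronium and sugammadex. A surgical cause does not remove the case, because the definitions disregard cause.

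**Would it come to light?** The plan provides for this, with calls on postoperative days 1 and 7 and a case-file review at days 17-21 (*Registration of adverse events*).

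**What does each rule then require?**

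| Rule | Instruction for this case | Exception for surgical cause or for seriousness? |
|---|---|---|
| *Registration of adverse events* | Follow up and record on the CRF | None |
| *Reporting Procedures* (i) | Is an AE and an SAE | None |
| *Reporting Procedures* (ii) | Forward within two business days | None |
| Local investigator's duty | Report to the sponsor at once | None |
| *Side effects/events that will not be registered* | Do not register | None |
| End-of-trial list, first sentence | Include, as an SAE | None |
| End-of-trial list, closing sentence | Included if registered | Follows from registration |

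**Do the passages reconcile themselves?** No. The exclusion does not say that it yields to the SAE rules, and the SAE rules do not say that they override it. The two sentences on the final list repeat the conflict: the first brings in all SAEs, while the second describes the contents as registered events.

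**Does the limit to certain attribution resolve it?** It narrows the set of events concerned. It does not remove the conflict, since certainty about a surgical cause is no ground for omission under definitions that disregard cause.

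**How many events?** The documents give no rate of serious surgical or postoperative events, so a count would rest wholly on an assumed rate. None is offered here.

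**The case against.** The strongest reply is that the serious-event rules form a separate track and remain fully in force. The exclusion never mentions SAEs. It opens in general terms, about the normal course of anaesthesia and surgery, and an infection needing admission after outpatient surgery is arguably outside that course. Item (v) of *Reporting Procedures* also commits the investigator to all regulatory reporting of AEs, SAEs and SUSARs. The final-list paragraph names SAEs, and its closing sentence says the list holds all registered events without saying that it holds only those. On this reading the exclusion merely trims routine, non-serious registration.

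Much of this stands. It is a natural reading and may be what was intended. It also defeats the inference a reader might draw that serious wound infections would certainly be lost and that none would reach the list; the text does not establish that. But the intention is not written down. The wound sentence is separate from the opening one and is unconditional, and forwarding a case to the company does not make it a registered event.

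A reader might also infer that the exclusion hides a harm of the intervention. The documents do not support this. They do not name wound infection as a risk of rocuronium, sugammadex or depth of block. The background credits the laparoscopic approach with fewer wound complications, but both groups have laparoscopic surgery. That conditions and duration differ between groups is the trial's hypothesis, not a finding.

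Nor do the documents show that attribution is made by someone who knows the allocation. They do not say who judges certainty. *Blinding* allows the local investigator to be unblinded during the operation but keeps surgical, recovery and ward staff blinded. *Ethical considerations* mentions routine unblinding after the operation. Unblinded attribution is therefore possible but not stated.

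**Conclusion.** The point holds as a conflict between stated rules. The exclusion covers events ascribed with certainty to the operation or to postoperative treatment and makes no exception for serious ones. The AE and SAE definitions, the forwarding duty, the CRF rule and the sponsor-reporting rule contain no exception for cause. For a wound infection requiring admission they give opposite instructions, and such an event could be left off the end-of-trial list to the ethics committee and the Danish Medicines Agency.

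The loss is possible rather than certain, and its size cannot be computed from the documents. The conclusion assumes only that such an event can occur and that staff might apply the exclusion as written. The primary outcome, sample size, error rate and analysis are not affected. It should be corrected because it concerns the completeness of serious-event reporting and costs very little to put right.

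**What to change.** Add to *Side effects/events that will not be registered* a statement that the exclusion applies only to non-serious events. It should say that every event meeting the SAE definition in *Reporting Procedures* (i) is registered, forwarded and placed on the end-of-trial list, whether it is attributed to the operation, to postoperative treatment or to anything else. A cross-reference from *Registration of adverse events* to the narrowed exclusion would reconcile the CRF rule for non-serious events too.

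The cost is slightly more adverse-event paperwork. No visits are added, because the planned calls and file review already supply the information. Tabulating wound infection by group is optional and is not needed to resolve the conflict.

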Intervention medicine is prepared in the medicine room before the operation. This is done under double control by the investigator who also performed the randomization. Labels named “project medicine” will be placed on the syringes.

Randomization group will be noted on a sheet (NMB sheet), on which other data concerning neuromuscular blockade (NMB) will also be noted. On this sheet will also be noted the quantity of rocuronium and sugammadex administered, as well as values measured with TOF-Watch. This will not be noted on the anesthesia form. After conclusion of anesthesia the NMB sheet will be placed in the accompanying envelope, which is sealed and placed in a locked drawer where only investigators of the study has

access to. If there is a need for emergency unblinding the envelope is placed in this drawer: The envelope must only be opened, if it is considered strictly necessary to know which group the patient belongs to with respect to further treatment. This will happen after agreement with the investigator responsible for the trial and the phone number of the investigator is written on the envelope. Motivation for broken seal shall be included in the Case Report Form (CRF).

At the front of the patient's case file a sheet will be placed, which states that the patient is included in the trial.

The patient will at no time during hospitalization and possible recurrences follow up (regarding recurrences) be informed about treatment group allocation. The patient may however be informed of this upon conclusion of data collection.

The surgeon, will be blinded to treatment group allocation during the operation.

The anesthesia personnel, including local investigator, who anaesthetize the patient, may during inception and operation not be blinded, because the degree of the neuromuscular block shall be adjusted.

Surgical personnel, recovery ward personnel and ward personnel will be blinded to treatment group allocation.

Perioperative treatment:

Monitoring:

The patient will be monitored with ECG, non-invasive blood pressure, oxygen saturation, sleep depth measure with BIS [BiSpectral Index], and temperature sensors.

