Inclusion of 1-2 patients per week is expected corresponding to duration of inclusion of approximately 24 months. Inclusion: Planned to go on in the period from February 2015 to February 2017. Inclusion of patients will be stopped when the desired number of patients is achieved. The trial will be counted as concluded, when the last patient has registered with the primary endpoint.

Data analysis and reporting: from April to May 2017.

Ethical considerations:

Laparoscopic herniotomy is presently conducted at Gentofte Hospital with an intraabdominal pressure of 12 mmHg and sometimes with use of a small quantity of muscle relaxant for intubation.

It is not considered an inconvenience to use large doses of muscle relaxant, as the effect of this is fully reversed by sugammadex at the end of the anesthesia. Anesthesia and surgery will follow guidelines apart from the dosage of muscle relaxants.

We think that it is justifiable that information about the use of muscle relaxants/antidotes be stored in a sealed envelope in the patient record with respect to the blinding. There is an option to break the seal on the envelope in an emergency situation. Routinely unblinding of the included patients will be done after the operation. Sugammadex is considered active in the first 24 hours, but the intervention will be considered to be over.

The possible benefit in this trial is to investigate whether deep neuromuscular blockade gives better surgical space conditions at pneumoperitoneum 12mmHg in patients > 18 years old undergoing laparoscopic umbilical, -linea alba and incisional herniotomy.

Protocol
The hernia study
September 16. 2016

Informed consent will be obtained before the patients arrive to the operation ward. We thereby wish to avoid having the patient make a decision about participation in the trial, in the stressed environment an operation ward is often experienced as for a patient before an operation. The inclusion and exclusion criteria used will ensure that we only investigate patients who will be able to tolerate being treated according to the two strategies. Intervention with respect to possible complications from this, are not unchanged either.

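### The emergency-unblinding envelope has two incompatible storage places, and routine unblinding after surgery contradicts patient blinding through recurrence follow-up

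*Combined protocol and SAP*

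**What the plan says.** **Blinding.** The NMB sheet carries the randomization group, the rocuronium and sugammadex quantities given and the TOF-Watch values. These are deliberately left off the anesthesia form. After anesthesia the sheet goes into an envelope "which is sealed and placed in a locked drawer where only investigators of the study has" access. The same paragraph makes this the emergency envelope: "If there is a need for emergency unblinding the envelope is placed in this drawer". It may be opened only if strictly necessary and by agreement with the responsible investigator, and "the phone number of the investigator is written on the envelope". The one item placed in the patient's file is a notice of participation: "At the front of the patient's case file a sheet will be placed, which states that the patient is included in the trial".

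On who stays blinded, the section says of the patient: "The patient will at no time during hospitalization and possible recurrences follow up (regarding recurrences) be informed about treatment group allocation". Disclosure to the patient is allowed only once data collection has ended. It says of staff: "Surgical personnel, recovery ward personnel and ward personnel will be blinded to treatment group allocation".

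**Ethical considerations.** Information on relaxants and antidotes is to be "stored in a sealed envelope in the patient record with respect to the blinding", and "There is an option to break the seal on the envelope in an emergency situation". The next sentences say that included patients are unblinded as a matter of routine once the operation is over, and that sugammadex is regarded as active for 24 hours.

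**Outcomes.** Recurrence at 2 years, assessed by a surgeon, is listed among the secondary outcomes that compare Group A with Group B.

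**The concern.** Two things need to be settled before the first patient leaves the operating room: how a treating doctor learns what was given, and who may know the allocation until recurrence has been assessed. The protocol answers each question twice, differently.

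On access, the drawer version is circular for anyone outside the trial. Opening the envelope needs an investigator's agreement, and the stated place to find the investigator's number is on the envelope in the drawer. What the envelope holds cannot be fully deduced from knowing that the patient is in the trial. The sugammadex quantity depends on the level of block, placebo reversal is possible, and Group B may also have received mivacurium.

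On blinding, recurrence is a between-group comparison read 2 years after surgery. If allocation is disclosed routinely after the operation, the patient blinding promised for that follow-up is lost by design and not by accident. A patient who knows the sequence might respond differently to the follow-up invitation or report symptoms differently.

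**Working it through.** No sample size, rate or test statistic enters this point, so there is nothing to compute and no figure in the plan to reproduce. The check is a side-by-side reading.

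| Item | Blinding | Ethical considerations |
|---|---|---|
| Content | Group, rocuronium and sugammadex quantities, TOF values | Use of muscle relaxants and antidotes |
| Purpose | Emergency unblinding | Emergency breaking of the seal |
| Location | Investigators' locked drawer | Patient record |
| Contact number | On the envelope | Not mentioned |
| Unblinding of patients | Not before data collection ends | Routinely, after the operation |

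**1. Is it the same envelope?** Content and purpose match. The only other sealed item is the copy of the randomization list held by the coordinating investigator (Randomization section). That copy gives the group but not the quantities administered, and it is not placed in the record. No section mentions two envelopes or a duplicate NMB sheet. The two locations therefore conflict.

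**2. What follows from each location?** In the drawer, concealment is well protected, but staff who are not investigators have no written route to the envelope or to the number on it. In the record, staff using the file can reach the envelope, and concealment then depends on the seal. Neither section says how both aims are met.

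**3. Over what period does access matter?** The protocol's own window is 24 hours for sugammadex. The Surgical method section says operations are outpatient procedures, so part of that window can fall after discharge, when a patient may be seen by staff with no link to the trial.

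**4. Do the unblinding statements agree?** Blinding rules out telling the patient during the hospital stay or recurrence follow-up. Ethical considerations sets routine unblinding after the operation and gives no other time. If that sentence means informing patients, it contradicts Blinding outright. If it means opening the code to staff only, it still conflicts with the blinding of recovery and ward personnel.

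**5. Which outcomes are exposed?** The workspace ratings, suturing conditions, contractions, insufflator alarms and operating time are all recorded during surgery. The envelope is sealed only after anesthesia. Among the listed outcomes, only 2-year recurrence comes after that moment.

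**The case against.** The strongest reply is that the practical consequences are small, and much of it stands.

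- **A reader might infer that urgent access is blocked.** The documents do not support that. The anesthesia personnel and local investigator are unblinded, and the coordinating investigator holds the sealed list and is the contact named in the participant information. Patients are also encouraged to contact the local investigator. Requiring an investigator's agreement is consistent with investigator-only custody. What remains is that none of these routes is written into the emergency procedure, and the list does not give the quantities.
- **A reader might infer that treating staff would not know which drugs were used.** Rocuronium is given in both groups, and sugammadex normally is too. The case-file sheet identifies a trial patient. The envelope mainly conceals sequence, quantity and timing.
- **A reader might infer that an envelope in the record unblinds the surgeon who assesses recurrence.** An intact seal still conceals allocation, and a broken seal must be explained in the CRF. Nor does any section say that the 2-year assessor is blinded. Blinding covers the operating surgeon during the operation and lists surgical personnel without a time frame. Only patient blinding is stated for that follow-up.
- **A reader might infer that all 34 patients are affected.** Each has an envelope, but the access gap matters only in an emergency where its contents are needed, and no rate is given.

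None of this removes the conflict over location or the conflict over when patients are unblinded.

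**Conclusion.** The point holds as an internal inconsistency of minor weight. The two sections give incompatible locations for what reads as one emergency envelope, and incompatible times for unblinding patients. The second conflict is the more direct threat to follow-up blinding, because it does not depend on anyone breaking a seal.

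The size is bounded but cannot be quantified from the documents. The primary outcome and the intraoperative secondary outcomes are unaffected. The issue concerns emergency access, chiefly in the first 24 hours, and blinding for the secondary recurrence outcome, which is due for separate publication. Access is impeded rather than prevented, and harm to blinding is a risk rather than a demonstrated bias.

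The conclusion assumes that both sections mean the same envelope and that no separate site procedure resolves the difference. The documents mention none.

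**What to change.** 1. In both sections, state one location for the envelope and one access procedure: who may open it, by whose agreement, and how that person is reached at any hour. It should work for at least the 24 hours in which the protocol regards sugammadex as active, including after same-day discharge. Moving the envelope to locked storage at discharge would not by itself meet this.
2. Print the investigator's contact number on the participation sheet already placed at the front of the case file, so that it no longer depends on reaching the envelope.
3. Delete the routine-unblinding sentence in Ethical considerations, or re-time it to fall after the 2-year recurrence assessment, in agreement with Blinding. Name that assessment explicitly instead of referring to study completion, because the End of study section closes the study at the primary endpoint.
4. While editing, state whether the surgeon who assesses recurrence is blinded.

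The cost is a few sentences in two sections and one line on an existing sheet. No dose, schedule, sample size or analysis changes. The documents do not say whether the investigator's number is answered out of hours. If it is not, someone must be named to cover it.
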